8.2.4.5. Post-Treatment

For patients who discontinue treatment with Plegridy, all follow-up visits will be conducted according to local clinical practice. Patients' participation in the study is independent of potential stopping treatment with Plegridy. Analysis of this patient data will be part of the exploratory analysis.

8.2.4.6. Concomitant Medications

A concomitant medication is any drug or substance administered after the first recorded dose of Plegridy.

As a long-term, observational study to evaluate effectiveness and safety in patients treated in the postmarketing setting, no restrictions on concomitant medications are associated with this study.

All concomitant medications will be recorded in the patient's eCRF according to instructions for eCRF completion. Concomitant medications will be recorded at baseline and at each data collection period until the end of follow-up in order to evaluate their potential influence on the outcomes of interest.

8.2.4.7. Long-Term Follow-Up

After enrollment, the Prescribing Physician will collect patient information during routine clinical visits as described in [Section 8.3](#). For the purposes of this study, routine clinical visits are defined as any visit scheduled per local standard of care. The collected information for each patient will be sent to the CRO managing the study (IQVIA, see [Section 8.5](#)) through the EDC system at baseline, approximately every three months (\pm four weeks) for the first year of follow-up and approximately every six months (\pm four weeks) for Year 2 through Year 5 of follow-up after enrollment. If the CRO does not receive completed data from the physician on a patient for whom follow-up is expected, the CRO will contact the site to remind them to complete the required data.

CONFIDENTIAL

The information contained herein may not be used, disclosed, or published without the written consent of Biogen MA Inc.

PROs may be completed by patients either electronically or on paper. PROs can be accessed electronically via a secure, personalized link either at the time of a routine clinic visit or outside of the clinic within four weeks of the routine visit. Alternatively, the PROs can be completed on paper at the time of a routine clinic visit. PROs will be collected at baseline (enrollment), approximately every three months for the first year of follow-up, and approximately every six months for Year 2 through Year 5 of follow-up after enrollment. If a patient does not complete the PROs during a routine clinic visit, the patient will be asked to complete the PROs within four weeks of each routine visit, if consistent with local regulations.

All information will be sent to the CRO electronically. The information received by the CRO will be stored in a secure database.

8.2.4.8. Non-initiation of Plegridy and Continued Participation in the Study

Consenting patients who are prescribed Plegridy, but do not take at least one dose of Plegridy after enrollment into the study, will continue to be followed for up to 60 months after enrollment, unless death, withdrawal, or loss to follow-up occurs.

Patients who do not initiate treatment with Plegridy can start Plegridy treatment as part of routine clinical practice at any time.

8.2.4.9. Discontinuation of Plegridy

Patients who discontinue treatment with Plegridy will continue to be followed for the duration of the study or until death, withdrawal, or until they are lost to follow-up. The Prescribing Physician will record the primary reason for Plegridy discontinuation, if applicable. Information will be collected at the time of a routine clinical visit following [Table 4](#) and as described in Section [8.3.4](#) through 30 days after last dose.

It should be noted that patients who discontinue treatment with Plegridy should continue to be followed in the study. These patients are allowed to restart Plegridy at any time during the study. Once a patient has restarted Plegridy, the information collected should follow [Table 4](#) and as described in Section [8.3.3](#).

8.2.4.10. Withdrawal of Subjects from the Study

Patients must be withdrawn from the study for either of the following reasons:

- The patient withdraws consent.
- The patient is unwilling or unable to comply with the protocol.

The reason for the patient's withdrawal from the study must be recorded in the patient's eCRF.

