8.2. Setting

8.2.1. Inclusion Criteria

To be eligible to participate in this study, patients must meet the following eligibility criteria at the time of enrollment:

1. Patient and or legal representative is willing and able to understand the purpose and risks of the study and provide signed and dated informed consent and authorization to use protected health information (PHI) in accordance with national and local patient privacy regulations.
2. Patient with MS who is newly, or is currently, prescribed Plegridy according to local label including patients who participated in Study 105MS302 or Study 105MS303.
3. Patient age 18 years or older.
4. Patient willing and able to complete PROs with minimal assistance.

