8.2.4. Overall Study Duration and Follow-Up

The study period will consist of enrollment and a follow-up period. Patient participation in the study will be for up to five years (60 months) from enrollment. The planned duration of the study is approximately seven years (87 months), which includes over two years (27 months) for patient enrollment and a maximum of five years (60 months) of follow-up per patient. Patients will be followed for up to five years or until death, withdrawal, or loss of follow-up, whichever occurs first. Follow-up is planned regardless of whether patients discontinue treatment with Plegridy.

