8.2.4.11. Premature Withdrawal From Study

Patients may withdraw consent to participate in the study at any time with no effect on their medical care or access to treatment. If a patient is withdrawn prior to completing the study follow-up period, any known reason for withdrawal should be documented in the eCRF. All information already collected as part of the study will be retained for the

CONFIDENTIAL

The information contained herein may not be used, disclosed, or published without the written consent of Biogen MA Inc.

analysis; however, no further efforts will be made to obtain or record additional information regarding the patient.

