16.1. Schedule of Events

Relevant data time points for the study are presented in the Schedule of Events provided in [Table 4](#) below. All data elements will be collected from information routinely recorded in the medical record, or will be prospectively recorded by the Prescribing Physician for the purposes of the study. No visits or examinations, laboratory tests or procedures are mandated as part of this study. Patient-reported outcomes (PROs) will be collected directly from the patient either electronically via secure, personalized link or on paper at the time of a routine clinic visit. If a patient does not complete his/her PROs during the clinic visit then he/she can complete the PROs electronically via the secure, personalized link within four weeks of his/her routine clinical visit. Refer to [Section 8.2.4.7](#) for details regarding PRO collection, and [Section 8.3](#) for details regarding the data elements to be collected. After enrollment in the study, all clinical data are captured in accordance with routine visits per local clinical practice and label regardless of treatment choice.

Table 4: Schedule of Events: POP 105MS401

Assessments ¹	Baseline ²	Every 3 months (±4 weeks) in follow-up Year 1	Every 6 months (±4 weeks) in follow- up Years 2-5	Study Discontinuation ³
Date of Signed Informed Consent	X			
Site and Prescribing Physician Characteristics	X			
Demographic characteristics	X			
Relevant medical history and co-morbidities	X			
MS disease history	X			
History of FLS on previous IFN therapy	X			
Results of latest brain MRI scan	X	X	X	
Prior use and duration of immunomodulatory, immunosuppressive (including corticosteroids), and anti-neoplastic agents, and other approved MS therapies	X			
Prior use and duration of all other concomitant medications	X			
Participant in Study105MS302 or Study 105MS303	X			

CONFIDENTIAL

The information contained herein may not be used, disclosed, or published without the written consent of Biogen MA Inc.

Assessments ¹	Baseline ²	Every 3 months (±4 weeks) in follow-up Year 1	Every 6 months (±4 weeks) in follow- up Years 2-5	Study Discontinuation ³
Plegridy prescription information: start and stop dates, initial dose, dose reductions or escalations, prescribed dosing frequency, duration of use, reason for discontinuation, if applicable	X	X	X	X
CBC with differential, if consistent with local practice	X	X	X	X
Other laboratory tests recommended in local label	X	X	X	X
Concomitant use of medications	X	X	X	X

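### Mandatory withdrawal of patients who are unable to comply stops follow-up that needs nothing from the patient, and the loss may depend on disability or illness

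*Protocol*

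**What the plan says.** Section 8.2.4.10 of the Protocol reads: "Patients must be withdrawn from the study for either of the following reasons". The first reason is withdrawal of consent. The second is: "The patient is unwilling or unable to comply with the protocol". Neither unwillingness nor inability is defined.

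After withdrawal, section 8.2.4.11 says that "no further efforts will be made to obtain or record additional information regarding the patient", and footnote 3 of Table 4 repeats this. The same section keeps earlier data: "All information already collected as part of the study will be retained for the" analysis. Sections 10.2.2 and 10.2.4 end SAE collection at premature withdrawal from the study.

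Little is asked of the patient. Section 16.1 states: "No visits or examinations, laboratory tests or procedures are mandated as part of this study". Sections 8.2.4.8 and 8.2.4.9 keep patients in the study even if they never start Plegridy or stop it. PROs are scheduled at every time point in Table 4. Inclusion criterion 4 in section 8.2.1 reads "Patient willing and able to complete PROs with minimal assistance", under the stem that "patients must meet the following eligibility criteria at the time of enrollment".

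**The concern.** The rule uses an undefined patient attribute to end data capture that does not depend on the patient. SAEs, relapses, EDSS or neurologic assessments and treatment data are entered by the physician from routine care. A patient who still attends the clinic but can no longer manage the questionnaires, or refuses them, could be withdrawn by a site applying 8.2.4.10 literally. From then on nothing more is recorded.

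In a five-year study of a disabling disease, inability is plausibly linked to progression, relapse or serious illness, which is what the co-primary endpoints measure. Such a loss is informative, and the SAP cannot repair it, because data that were never collected cannot be analyzed.

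**Working it through.** **1. The plan's own precision.** Section 8.6.7 gives N = 1100, dropout up to 20%, expected one-year cNEDA 0.684, and a 95% half-width of 0.027 to 0.031. The formula is 1.96 × √(p(1−p)/n).
- n = 1100: 1.96 × √(0.684 × 0.316 / 1100) = 0.0275.
- n = 1100 × 0.80 = 880: 1.96 × √(0.684 × 0.316 / 880) = 0.0307.

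The stated range is reproduced. The calculation treats dropout only as a smaller n and does not consider dropout related to outcome.

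**2. What there is to comply with.** Visits, examinations, tests and procedures are not mandated (16.1), and treatment is not required (8.2.4.8, 8.2.4.9). PROs are scheduled throughout (Table 4), and section 8.2.4.7 has patients asked to complete missed PROs within four weeks of the visit. PROs are therefore the most natural object of the second bullet. Nothing in the protocol names them there, and nothing excludes them.

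**3. Effect on cNEDA (illustration).** Let w be the share withdrawn under the rule before any event is recorded, q their true cNEDA proportion, and 0.684 the proportion among the rest. The protocol gives neither w nor q.

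The true overall value is (1−w) × 0.684 + w × q. If withdrawn patients leave the denominator, the observed value is 0.684 and the overstatement is w × (0.684 − q), in percentage points:

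| w | q = 0 | q = 0.342 (half of 0.684) | q = 0.684 |
|---|---|---|---|
| 2% | 1.4 | 0.7 | 0 |
| 5% | 3.4 | 1.7 | 0 |
| 10% | 6.8 | 3.4 | 0 |
| 20% (whole dropout allowance) | 13.7 | 6.8 | 0 |

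At q = 0 the overstatement passes the planned half-width when w exceeds 0.0275/0.684 = 4.0% to 0.031/0.684 = 4.5%.

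If withdrawn patients instead stay in the denominator and count as event-free, the overstatement is w × (1 − q). At w = 5% this is 5.0 points for q = 0 and 0.05 × 0.658 = 3.3 points for q = 0.342.

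Events recorded before withdrawal reduce the bias. Take 5% withdrawn, none truly event-free, half of them with an event already recorded and counted, and the other half leaving the denominator. Observed cNEDA is 0.95 × 0.684 / (0.95 + 0.025) = 0.6665, the true value is 0.6498, and the bias is 1.7 points. If all had a recorded event, the bias is zero.

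**4. Effect on SAE incidence.** Section 8.6.4.2 divides by all patients in the analysis population, so a withdrawn patient stays in the denominator. If a share s of those withdrawn have their first SAE only afterwards, the five-year proportion is understated by w × s. This concerns mainly patients still on Plegridy, because section 10.2.2 can be read as ending SAE collection 30 days after the last dose for those who stop.

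**5. Sustained progression.** Section 8.6.5.4 requires progression to last at least six months. A worsening first seen shortly before withdrawal cannot be confirmed.

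**6. Time left to act.** Enrollment ended in January 2017, so 60 months of follow-up runs to January 2022. From Version 5.0 (April 2019) up to about 33 months remain for the last patients enrolled.

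**The case against.** A reader might infer that the rule removes disabled patients from both co-primary endpoints. The documents do not support that. Section 8.2.4.11 keeps everything already collected, and the analysis populations in 8.6.4.1 and 8.6.5.1 do not exclude withdrawn patients. The incidence rate is adjusted for duration of follow-up. Follow-up is cut short, but the patient is not deleted.

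A reader might also take criterion 4 as a continuing condition of participation. It applies at enrollment only. Section 8.2.4.7 words PRO completion permissively, the adherence questionnaires (16.5, 16.6) allow caregiver help, and the resource questionnaire (16.4) lists family and paid caregivers as respondents. The link from 8.2.4.10 to PROs is a plausible reading, not an express rule. Because so little is demanded, the rule may seldom be used.

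Nor is there a formal contradiction with the follow-up aim, since section 8.2.4 carries the exception: "Patients will be followed for up to five years or until death, withdrawal, or loss of follow-up, whichever occurs first".

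Finally, the larger cNEDA shifts stack assumptions: all withdrawn under this one bullet, all with disease activity, none of it recorded. The 0.684 is a one-year figure, while the mechanism works over five years. Treatment of the cNEDA denominator may be left to the SAP, which was not available here. Loss of unconfirmed progression follows any early exit, and the six-month requirement is written for the secondary endpoints.

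All of this limits the claim. What stands is that withdrawal is mandatory, the trigger is undefined, and record-based data stop for no methodological reason.

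**Conclusion.** The point holds as a risk of avoidable, outcome-related loss to follow-up. Sections 8.2.4.10 and 8.2.4.11 together can end collection of SAEs, relapses and disability data that the physician could still supply. The likely direction is an understated five-year SAE proportion and overstated long-term cNEDA.

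The size is unknown, because the protocol gives no rate for this rule. The 0 to 3.4 points at w = 5% rests on 0.684 among the remaining patients, no event recorded before withdrawal, and withdrawn patients leaving the denominator. It is zero if those withdrawn fare like the rest. It is an illustration, not an estimate. The problem merits correction because the rule brings no analytical benefit and the data would otherwise be available.

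**What to change.** In section 8.2.4.10, either make withdrawal of consent the only mandatory reason, or keep the second bullet and limit what it ends. Suggested addition: inability or unwillingness to complete PROs ends PRO collection only; SAE, relapse, EDSS or neurologic, and treatment data continue to be collected from the medical record, under the existing consent, for up to 60 months. Record the date and the reason that PROs stopped. Align section 8.2.4.11 and footnote 3 of Table 4.

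The cost is a protocol amendment with ethics submission (section 9.3), possibly a consent form change, and a letter to about 160 sites. No visits or procedures are added. There will be more missing PRO data among retained patients. The change acts only on follow-up still to be collected and does not recover patients already withdrawn.

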8.2.4.11. Premature Withdrawal From Study

Patients may withdraw consent to participate in the study at any time with no effect on their medical care or access to treatment. If a patient is withdrawn prior to completing the study follow-up period, any known reason for withdrawal should be documented in the eCRF. All information already collected as part of the study will be retained for the

CONFIDENTIAL

The information contained herein may not be used, disclosed, or published without the written consent of Biogen MA Inc.

analysis; however, no further efforts will be made to obtain or record additional information regarding the patient.

8.2.4.12. Lost to Follow-Up

If a patient has not been in contact with the Prescribing Physician for 12 months following his or her last routine visit, the site will contact the patient by telephone to assess the patient's interest in continuing study participation. If the site is unable to contact the patient, a follow-up attempt must be made. A site may consider a patient lost to follow-up after three failed and documented contact attempts. If a patient's status is determined to be lost to follow-up, this must be recorded on the eCRF. If a physician ascertains a patient has died, the death should be recorded and reported as described in Section [10.2.4.1](#).

8.2.4.13. Subject Transfers

In the event that a patient wishes to transfer to a different physician, Biogen will attempt to find another site at which the patient can continue to participate in the study. If the patient continues care with a physician who is not participating in the POP study, Biogen may choose to include the new site in the observational study program, if feasible.

8.2.4.14. Study Stopping Rules

Biogen may terminate this study at any time, after informing participating Prescribing Physicians. Prescribing Physicians will be notified by Biogen or designee if the study is placed on hold, completed, or closed.

8.2.4.15. End of Study

The end of study is last patient, last visit for final collection of data for the primary outcome. The end of study will occur a maximum of five years (60 months) after the last patient is enrolled into the study.

8.2.5. Description of Source Population (new subheading)

The source population for this study includes patients with MS who are newly or currently prescribed Plegridy under routine clinical practice, and according to the local label, or who were previously participating in Study 105MS302 or Study 105MS303.

8.3. Variables

8.3.1. Site and Prescribing Physician Characteristics

The following data will be collected from the site and Prescribing Physician:

- Site characteristics (e.g., community or academic/institutional center, size, geography)
- Prescribing Physician characteristics (e.g., specialty, years in practice, current EDSS certification)

CONFIDENTIAL

The information contained herein may not be used, disclosed, or published without the written consent of Biogen MA Inc.

Refer to Section 16 for the timing of assessments.

Refer to the Study Reference Manual for details regarding EDSS certification.

8.3.2. Demographics, Baseline Disease Characteristics, and Treatment History

The following data will be collected at baseline for all enrolled patients:

- Documentation of signed informed consent.
- Demographic: age at enrollment (years), sex, race (where allowed by local regulation).
- Relevant medical history and co-morbidities: assessment of clinically significant medical and surgical history and concomitant diseases, and known cardiovascular risk factors (e.g., smoking, alcohol consumption, patient and family history of high cholesterol, high blood pressure, cardiac disease, peripheral artery disease, arrhythmia, cerebrovascular disease, and diabetes mellitus).
- MS disease history (type of MS, relapse history, and the latest EDSS score based on last neurologic examination conducted prior to enrollment) and the results of the latest brain MRI scan, which may include lesion count (if available).
- Prior use and duration of therapies for MS (if any; e.g., start and stop dates, initial dose, dose reductions or escalations, prescribed dosing frequency, reason for discontinuation).
- Prior use and duration of immunomodulatory, immunosuppressive (including corticosteroids), and anti-neoplastic agents (if any; e.g., start and stop dates, initial dose, dose reductions or escalations, prescribed dosing frequency, reason for discontinuation).
- Prior use and duration of all other concomitant medications (e.g., start and stop dates, initial dose, dose reductions or escalations, prescribed dosing frequency, reason for discontinuation).
- History of FLS on previous IFN therapy (e.g., history of chills, body aches, pyrexia, myalgia, or muscle aches).
- Ambulation status at time of initiating Plegridy.
- MRI results (e.g., lesion counts), if available.
- CBC with differential, if consistent with routine clinical practice and local regulations.
- Other laboratory tests recommended in local label (e.g., liver and renal function tests, urinalysis) if consistent with routine clinical practice and local regulations.
- Concomitant use (i.e., at enrollment) of immunomodulatory, immunosuppressive (including corticosteroids), and anti-neoplastic agents, and other approved MS therapies (if any).
- Concomitant use (i.e., at enrollment) of non-MS therapy medications (if any).

CONFIDENTIAL

The information contained herein may not be used, disclosed, or published without the written consent of Biogen MA Inc.

- EDSS information (including Functional System Scores and Ambulation scores), based on neurological examination at enrollment, when collected as part of routine clinical practice (i.e., not specifically performed for the study).
- Neurologic assessment (as per local practice and regulation) if EDSS is not used in routine clinical practice.
- [REDACTED]
- Patient assessment of the following outcome measures, if consistent with local regulations:
 - EQ-5D-3L: Refer to Section 16.2 , Appendix 1.
 - FLS Assessment: Refer to, Appendix 2.
 - Healthcare resource consumption questionnaire: Refer to Section 16.4, Appendix 3.
 - Treatment adherence questionnaire: Refer to Section 16.5 and Section 16.6, Appendices 4 and 5.
 - FLS-VAS*: Refer to Section 16.7, Appendix 6.
 - [REDACTED]

** Note: If a patient selects “Absent” for Question 1 of the FLS Assessment, then the FLS-VAS does not need to be completed for that patient.*

- Pregnancy status (female patients)
- Nursing status (female patients)
- Participant of Study 105MS302 or Study 105MS303.

Refer to Section 16.1 for the timing of assessments.

